Subject Population	

• No age limitations

• Patients with ostium secundum ASD measuring 8-35 mm by stop-balloon sizing

• Inter-atrial shunting with evidence of right heart volume overload, demonstrating the need for septal defect closure

• Absence of concurrent cardiac conditions that could elevate morbidity/mortality beyond what is common for ASD

Number of Subjects	

• Training Cases: First 2 subjects per site

• Pivotal Phase: 125 subjects (non-training)

• Continued Access Phase: up to 535 subjects (non-training)

• Total Study Enrollment: up to 704 subjects

Number of Sites	Up to 22 sites in the U.S.
Coordination Principal Investigator	
[REDACTED]
 
[REDACTED]
 
[REDACTED]
 
National Principal Investigator, Pediatric
 
[REDACTED]
 
[REDACTED]
 
[REDACTED]
 
National Principal Investigator, Adult

Significant Inclusion Criteria	

• Patient has an ostium secundum ASD with evidence of left-to-right shunt and right ventricular volume overload.

• Patient has a defect size 8-35 mm as measured directly by stop-flow balloon sizing.

• Patient vasculature can accommodate the delivery system and procedural accessories.

• Patient can accommodate TEE or intracardiac echocardiography (ICE) probe for implant procedure.

• Patient is judged by the implanting physician to have adequate septal rims to retain the study device.

 
[REDACTED]
 
[REDACTED]

	

• [REDACTED]

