4.6 Baseline Characteristics

Subject demographics, clinical history, risk factors, and pre-procedure defect characteristics will be summarized using descriptive statistics for continuous variables (mean, standard deviation, number of observations, minimum and maximum) and discrete variables (percentage and count/sample).

CONFIDENTIAL INFORMATION

MD133254 Statistical Analysis Plan Template

Revision#: 1

Doc Type: GC

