4.7 Subgroup Analysis of Primary Endpoints

The primary endpoints will also be analyzed controlling for the following baseline covariates: age; sex; race and ethnicity.

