4.9 Additional Analyses

4.9.1 Wire Frame Fracture

In order to assess possible harm to subjects due to wire frame fracture, an additional analysis involving co-primary outcomes as well as device-related adverse events will be conducted by stratifying subjects with and without frame fracture. To preserve the temporal relationship, only those events that had an onset date on or following the possible timing of frame fracture will be counted in the frame fracture subgroup.

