4.9.3 Multivariable Modeling

Additional subgroup analyses may be performed based on variables identified to be significant predictors (p-value ≤ 0.05) in multivariate analyses. These subgroup analyses will be exploratory; no statistical inferences will be made.

CONFIDENTIAL INFORMATION

MD133254 Statistical Analysis Plan Template

Revision#: 1

Doc Type: GC

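### The wire-frame-fracture harm analysis in SAP 4.9.1 is a crude comparison of non-randomised groups, so any imbalance in defect size or age that is related to outcome could create or hide apparent harm

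*SAP*

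**What the plan says.** The purpose stated in SAP 4.9.1 is causal: "In order to assess possible harm to subjects due to wire frame fracture". Co-primary outcomes and device-related adverse events are to be compared in an analysis that "will be conducted by stratifying subjects with and without frame fracture". The one safeguard concerns timing: "only those events that had an onset date on or following the possible timing of frame fracture will be counted in the frame fracture subgroup". The section names no covariate, model, matching, baseline comparison, analysis set or cohort.

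Other parts of the plan bear on the point:

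- **Protocol, Study Summary.** There are no age limits, and defects are included when "measuring 8-35 mm by stop-balloon sizing". Follow-up fluoroscopy is scheduled at 6 and 36 months.
- **SAP 4.6.** "Subject demographics, clinical history, risk factors, and pre-procedure defect characteristics will be summarized", with no breakdown by fracture status.
- **SAP 4.7.** "The primary endpoints will also be analyzed controlling for the following baseline covariates: age; sex; race and ethnicity". Defect size is not listed and fracture is not mentioned.
- **SAP 4.9.3.** "Additional subgroup analyses may be performed based on variables identified to be significant predictors". This is optional and exploratory, and it is not tied to fracture.
- **SAP 4.1.2 and 4.1.3.** Composite clinical success is analysed in all enrolled subjects, including technical failures. Closure success is analysed in technical successes.

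**The concern.** Fracture occurs after implant and nobody assigns it, so nothing in the design makes the two groups alike. A baseline factor related to both fracture and outcome would confound the comparison. Defect diameter and age are reasonable candidates because the population ranges widely on both. They are also available without new data: age is a baseline characteristic and balloon sizing is part of the procedure.

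The timing rule deals with whether an event came before fracture. It does not deal with whether subjects whose frames fractured were at different risk from the start. Sections 4.6, 4.7 and 4.9.3 do not fill that gap for this comparison. By contrast, SAP 4.8 calls for a look at baseline and procedural differences when sites differ in outcome, and the fracture comparison has no such step.

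At stake is a device-safety statement. A crude difference could be read as harm from fracture when it reflects who had fractures, and the absence of a difference could be read as reassurance when it is not.

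**Working it through.** The plan gives no fracture rate, failure rate or effect size to reproduce, and the hypothesis and sample-size sections are redacted. **All rates below are assumptions.** Only N = 125 (SAP 3.4) and N = 460 (SAP 2.2) come from the documents.

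**1. Bias in the crude comparison.** Take two equal size classes, with failure risk 12% (large) and 4% (small), and let fracture be harmless. The risk in each fracture group is (share large × 12%) + (share small × 4%).

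For fracture in 40% of large and 10% of small defects:
- share large among fractured = 0.40/(0.40 + 0.10) = 0.8; risk = 0.8 × 12% + 0.2 × 4% = 10.4%
- share large among unfractured = 0.60/(0.60 + 0.90) = 0.4; risk = 0.4 × 12% + 0.6 × 4% = 7.2%
- crude RR = 10.4/7.2 = 1.44

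| Fracture, large / small | Fractured | Unfractured | Crude RR (true RR 1) |
|---|---|---|---|
| 40% / 10% | 10.4% | 7.2% | 1.44 |
| 10% / 40% | 5.6% | 8.8% | 0.64 |
| 30% / 20% | 8.8% | 7.7% | 1.14 |
| 20% / 30% | 7.2% | 8.3% | 0.87 |

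If fracture truly multiplies risk by 1.5, the first two rows become 15.6/7.2 = 2.17 and 8.4/8.8 = 0.95. In the second case real harm disappears.

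A second set of assumptions gives a similar picture. With failure 15% (large) and 5% (small), and large defects making up 70% of one group and 30% of the other, harmless fracture appears as 12.0/8.0 = 1.50 or 8.0/12.0 = 0.67.

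**2. What stratification recovers.** Use the first row at N = 125 and expected counts. The large class has 25 fractured (3.0 failures) and 37.5 unfractured (4.5). The small class has 6.25 fractured (0.25) and 56.25 unfractured (2.25). Each class has 62.5 subjects.
- Mantel-Haenszel numerator = 3.0 × 37.5/62.5 + 0.25 × 56.25/62.5 = 1.8 + 0.225 = 2.025
- Denominator = 4.5 × 25/62.5 + 2.25 × 6.25/62.5 = 1.8 + 0.225 = 2.025
- RR = 1.00, the true value, because size class is the only confounder in the example

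**3. Precision.** The same scenario has about 31 fractured subjects and 3.25 fractured failures. In simulation, about 79% of trials of 125 have at least one size class with no fractured failure. The central 95% of estimates runs from 0 to about 5 for the crude RR and from 0 to about 4 for Mantel-Haenszel. At 460 subjects the Mantel-Haenszel range is about 0.46 to 1.95. Separately, with 20-35% of 125 subjects fractured and a two-sided 5% test, power is about 20% for 10% vs 5% and 44-48% for 15% vs 5%.

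**4. Two biases that stratification leaves in place.**
- *Timing rule.* If a share s of the fractured group's events precedes the possible fracture time and these are dropped in that group only, a null effect appears as RR = 1 − s. For s of 25% to 75% that is 0.75 to 0.25. The same rule would apply inside every stratum.
- *Analysis set.* If the composite is compared in all enrolled subjects, technical failures count as failures in the unfractured group, although they have no implanted frame. With 2% technical failures, 20% of implanted subjects fractured and 8% other failures, the unfractured risk is (98 × 0.08 + 2.5)/100.5 = 10.3%, and RR = 8/10.3 = 0.78. With 5% and 35% it is (77.2 × 0.08 + 6.25)/83.4 = 14.9%, and RR = 0.54.

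**The case against.** **No shown link.** Nothing in the documents ties defect size or age to fracture, or either of them to outcome. The larger figures need a four-fold fracture gradient together with a three-fold failure gradient, and the weak case gives only 1.14 or 0.87. This stands. A reader might infer that the analysis is known to be confounded, or in which direction. The documents support neither inference. The table by fracture group is how the sponsor would find out.

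**Noise exceeds the bias.** At 125 subjects the sampling range swamps the distortion, and a stratified estimate cannot settle the harm question. This also stands. It argues against resting the harm statement on the stratified figure, but not against showing it beside the crude one.

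**Larger defects in the same section.** The one-sided timing rule and the unstated analysis set may bias more, and under the readings shown both push towards hiding harm. A reader might infer that a size-stratified result would be a valid harm estimate. It would not be while those two remain. Equally, repairing them would leave the confounding in place.

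**Descriptive status.** Section 4.9.1 has no hypothesis, test or decision rule. That limits the consequence, but a descriptive safety comparison can still mislead.

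**Other sources of control.** A reader might infer that this is the only planned look at fracture. That can be said only of the SAP text available. The protocol is supplied as a summary, the review board monitors safety trends throughout, and SAP 6.0 calls for output specifications that are not shown.

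**Conclusion.** The concern holds as a conditional one. SAP 4.9.1 asks a causal question and answers it with an unadjusted comparison of groups that were not randomised. No other visible SAP section supplies an adjustment. If defect size or age differs by fracture status and also bears on outcome, the crude result could show harm that is absent or miss harm that is present.

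On the assumed rates the distortion of a null effect runs from 0.64 to 1.50, with 0.87 to 1.14 under weak imbalance. The actual size and direction are unknown.

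The consequence is confined to the fracture safety inference. Neither co-primary test nor its conclusion depends on this analysis. The change is worth making because it is cheap and should need no new data collection. Even with it, the pivotal cohort alone is unlikely to support a firm statement on harm.

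**What to change.** Amend SAP 4.9.1 as follows:

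1. Tabulate balloon-sized defect diameter, age and, if recorded, implanted device size by fracture group.
2. Beside each crude comparison, give a Mantel-Haenszel risk ratio or difference with a confidence interval (exact where sparse). Stratify by two balloon-diameter classes with a cut-point set in advance and, separately, by child/adult. Label these analyses post hoc if fracture results have already been seen.
3. Report crude and stratified estimates together as descriptive. Do not base the harm statement on the stratified result alone.
4. Restrict the comparison to the technical success set. Say so explicitly for the composite, which SAP 4.1.2 otherwise places in all enrolled subjects.
5. Use the same time origin for counting events in both groups, for example a landmark or time-varying fracture status. Define the possible timing of fracture, given that follow-up fluoroscopy is scheduled only at 6 and 36 months.
6. State which cohort is used.

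The cost is a few sentences and one or two more tables. The downside is wide intervals with few events at N = 125, which is why stratification is kept to one factor at a time with two classes each.

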Study Duration	Total Study Duration: 5.5 years
Schedule of Events	
Screening Assessments (within 6 months of procedure)
 

• Physical exam

• Electrocardiogram (ECG)

• Echocardiogram (TTE or TEE)

 
Pre-Study Procedure (within 90 days of procedure)
 

• Echocardiogram (TTE)

 
Procedure
 

• Physical exam

• Stop-flow balloon sizing of defect

• Echocardiogram (TEE, TTE or ICE)

• Fluoroscopy

 
Pre-Discharge
 

• Electrocardiogram (ECG)

• Echocardiogram (TTE)

 
30 days and 6 months:
 

• Physical exam

• Electrocardiogram (ECG)

• Echocardiogram (TTE)

• Fluoroscopy (6 months for all Subjects)

 
Long-term follow-up at 12 months and 36 months included:
 

• Physical exam

• Electrocardiogram (ECG)

• Echocardiogram (TTE)

• Fluoroscopy (36 months for all Subjects)

 
A telephone follow-up occurred at 24 months

Additional Information	Echocardiography Core Lab, Independent Data Review Board (IDRB)

CONFIDENTIAL INFORMATION

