2.5 Study Endpoints

2.5.1 Primary Endpoints

Co-Primary Endpoint 1: 6-Month Closure Success is defined as a clinical residual defect status of occluded or clinically insignificant as determined by the Echo Core Lab at the 6-month evaluation among subjects with technical success.

Co-Primary Endpoint 2: Composite Clinical Success is evaluated at 6 months after index procedure among subjects with attempted study device closure and is defined as satisfying all of the following criteria:

1. Technical Success: Successful deployment and retention (at conclusion of index procedure) of a GORE® CARDIOFORM ASD Occluder
2. Safety Success:
 - Freedom from any Serious Adverse Event (SAE) related to the device or procedure, as adjudicated by the Independent Data Review Board (IDRB) through 30 days post-procedure
 - Freedom from device events (post-procedure embolization, device removal, or other device reintervention) from completion of the implant procedure through 6 months (180 days) post-procedure
3. Closure Success: A clinical residual defect status of occluded or clinically insignificant as determined by the Echo Core Lab at the 6-month evaluation.

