3.0 Study Data Collection

3.1 *Study Data Collection Intervals*

Refer to Section 5, Study Procedures and Evaluations, in the study protocol (MD151471).

3.2 *Study Interval Windows*

Subjects with successful study device implant will return for follow-up visits at 30 days, and at 6, 12, and 36 months. For the 24-month assessment, subjects will be contacted by telephone. Subjects considered Technical Failures (study device attempted but not implanted) are only required to complete a 30-day follow-up telephone assessment and will then be discontinued from the study. All intervals are calculated from the index procedure (day 0). The visit windows are calculated as the target day plus or minus the appropriate number of calendar days. The 6-month visit target is 180 days. The yearly visits are calculated on a 365-day year from index procedure.

30 Days	6 Months	12 Months (1 Year)	24 Months (2 Years)	36 Months (3 Years)
30 ± 14 days	180 ± 14 days	365 ± 60 days	730 ± 60 days	1095 ± 60 days

³ Hintze, J. (2013). PASS 12. NCSS, LLC. Kaysville, Utah, USA. www.ncss.com

3.3 *Independent Data Review Board (IDRB)*

Excerpt from section 9.7 of the study protocol:

During the course of the study, the IDRB will serve as both a Data and Safety Monitoring Board (DSMB) and Clinical Events Committee (CEC). As the DSMB, the IDRB will review aggregate safety data for the course of the study to monitor the incidence of SAEs and other safety trends that could warrant modification or termination of the study. As the CEC, the IDRB will adjudicate all site-reported adverse events through 30 days post-procedure for seriousness and relatedness of potential primary endpoint events. In addition, the IDRB will review and adjudicate all site-reported AEs related to arrhythmia for the course of the study. The IDRB Charter will outline the responsibilities and operating procedures of the Board.

3.4 *Site Enrollment Restrictions*

A maximum of 22⁴ investigative sites in the United States will participate in this study. One hundred twenty-five (125) non-training subjects will be enrolled in the Pivotal Phase of this study, with a limit of 10 non-training subjects enrolled at any single site during the Pivotal Phase. The first 2 subjects enrolled at each site will be considered training cases that do not apply to the above restrictions.

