4.5 Adverse Events

All site-reported AEs will be MedDRA coded and grouped by MedDRA System/Organ Class (SOC) and by MedDRA Preferred Term within SOC. AEs will also be grouped by seriousness (SAE vs. nonserious AE), primary relationship (device, procedure, study medication, and unrelated) and timing of onset (procedure, pre- and postdischarge). AEs will be summarized as rates given by subject-based binomial proportions. The numerator will be the count of subjects who experienced one or more episodes of the AE of interest in the time period of interest. The denominator will be the count of subjects free of the AE of interest through the time period of interest and with sufficient clinical follow-up for the time period of interest, plus the count of subjects in the numerator. Unless otherwise specified for a particular endpoint measure, all enrolled subjects in the analysis set of interest will be considered evaluable and will contribute to the denominator.

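### The frame-fracture harm analysis restricts events by date in the fracture subgroup only, so reports after 6 months can compare unequal time at risk

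*SAP*

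**What the plan says.** SAP section 4.9.1 gives its purpose as "In order to assess possible harm to subjects due to wire frame fracture". The method is "an additional analysis involving co-primary outcomes as well as device-related adverse events", stratified by fracture status, with one counting rule: "only those events that had an onset date on or following the possible timing of frame fracture will be counted in the frame fracture subgroup". The section gives no start for the other subgroup, no rule for a fracture subject's earlier events, and no definition of the possible timing.

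Elsewhere the origin is the procedure. SAP section 3.2 states: "All intervals are calculated from the index procedure (day 0"). The device-event window in section 2.5.1 runs "from completion of the implant procedure through 6 months (180 days) post-procedure". Under section 4.5, "AEs will be summarized as rates given by subject-based binomial proportions", so time at risk does not enter the rate.

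The protocol's schedule of events lists post-implant films at two visits only: "Fluoroscopy (6 months for all Subjects"), and again at 36 months. Fluoroscopy is also used at the procedure.

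**The concern.** The rule has a sound aim: an event that came before a fracture cannot have been caused by it. Applied to one side of a comparison of subject proportions, however, it shortens the time in which fracture subjects can have an event and leaves the comparator's time whole. A fracture with no effect can then look protective, and a real increase can be reduced or hidden.

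With films only at about 6 and 36 months, the fracture date is known only within a wide interval. How many events the rule removes therefore depends on a phrase that the section does not define. At stake is how a device-safety comparison is read in reports after 6 months.

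**Working it through.** The plan states no figure for this analysis, so there is none to reproduce. The calculation shows what the rule does to the risk ratio (fracture over no fracture).

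**From the documents.** Day 0 is the procedure. The films fall at day 180 and day 1095 (SAP section 3.2 targets; protocol schedule). Follow-up runs to 36 months (SAP section 2.2).

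**Assumed, not in the documents.** Risk *e* over days 0-30 is 0-5%, and later risk *l* is 1-3% per year at a constant hazard. The horizon is 36 months, first event per subject. The no-fracture subgroup is counted from the procedure.

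**Step 1: which fractures lose events.**
- Earliest possible date (last fracture-free image): a fracture first seen at 6 months dates back to the procedure and loses nothing, so its no-effect ratio is 1.00. A fracture first seen at 36 months loses everything before the clean 6-month film.
- Detection date: a fracture on the 6-month film loses everything before about day 180, including any 30-day serious adverse event in co-primary endpoint 2. One first seen on the 36-month film has nothing left to count before that visit.

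**Step 2: no true effect, counting from day 180.**
- S(180) = (1−e)(1−l)^(150/365) and S(1095) = (1−e)(1−l)^(1065/365).
- Apparent ratio R = [S(180)−S(1095)] / [1−S(1095)].
- At e = 3%, l = 2%: (0.9620−0.9145)/0.0855 = 0.0475/0.0855 = 0.555.

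**Step 3: hazard doubled after a fracture first seen at 36 months**, with fracture time uniform over days 180-1095.
- q = S(1095)/S(180). Mean survival after the 6-month film is A = q(1−q)/(−ln q).
- At e = 3%, l = 2%: q = 0.95062 and A = 0.95062 × 0.04938/0.05064 = 0.9270, so the risk is 0.0730.
- As the rule counts it: 0.9620 × 0.0730/0.0855 = 0.82. With both subgroups started at the film: 0.0730/0.0494 = 1.48.
- A simulation of 4,000,000 subjects per scenario gave 0.83 and 1.50.

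| e | l | S(180) | S(1095) | R, no effect | Hazard doubled, as counted |
|---|---|---|---|---|---|
| 0% | 1% | 0.9959 | 0.9711 | 0.86 | 1.28 |
| 0.5% | 1% | 0.9909 | 0.9662 | 0.73 | 1.09 |
| 1% | 3% | 0.9777 | 0.9058 | 0.76 | 1.12 |
| 3% | 2% | 0.9620 | 0.9145 | 0.56 | 0.82 |
| 5% | 1% | 0.9461 | 0.9225 | 0.30 | 0.45 |

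The first and last rows are the extremes of the grid. The no-effect column also applies, at 36 months, to fractures seen on the 6-month film under detection dating. The last column is for fractures first seen at 36 months under earliest-date dating.

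**Step 4: pooled, earliest-date reading, a quarter of fractures late (assumed).** 0.75 × 1 + 0.25 × R gives 0.89 at R = 0.555, and 0.83 to 0.96 for R from 0.30 to 0.86.

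**Step 5: where earlier events go** (e = 3%, l = 2%, 10% of subjects in affected fractures, no effect).
- Left out: 0.555.
- Left out, and the subject leaves the denominator: 0.577.
- Subject moved to no-fracture: 0.553.
- Event moved, denominators unchanged: 0.529.
- Event moved, fracture subjects in both denominators: 0.0475/(0.9 × 0.0855 + 0.1 × 0.0380) = 0.588.

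Only the last handling can exceed 1. With 50% fractured, e = 1% and l = 3%, it gives 0.0719/(0.5 × 0.0942 + 0.5 × 0.0223) = 1.23.

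**The case against.** The strongest reply is that the bias is narrow. Possible timing most naturally means the earliest date at which the fracture could have happened. On that reading fractures first seen at 6 months lose no events, and both co-primary outcomes end at 6 months. A reader might infer that the analysis supporting pre-market approval is distorted; on this reading it is not. This part stands.

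The size also depends on the assumed early risk. Section 4.9.1 names device-related events, and section 4.5 classes procedure-related events separately, so early device-related risk may be small. At 0-0.5% the no-effect ratio is 0.73 to 0.86 (0.93 to 0.96 pooled), and a true doubling reads about 1.09 to 1.28: weakened, not reversed. This stands too, and the range in the verdict includes it.

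A reader might infer that the rule always favours the device. Step 5 shows one handling of earlier events for which the direction is not fixed. A reader might also call the rule unworkable for closure, a status "as determined by the Echo Core Lab at the 6-month evaluation" with no onset date. The rule covers only events with an onset date, so the plain reading is that closure is simply stratified. That needs a clarifying phrase.

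Finally, the protocol is available only as a study summary, and SAP section 6.0 requires a specification for each output. The missing definitions may stand elsewhere. Section 4.9.1 cites no such source, and the one-sided rule is its own stated text.

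**Conclusion.** The point holds, within limits. The stated rule cuts events by date in one subgroup, sets no matching start in the other, and turns on an undefined date. If the no-fracture subgroup is counted from the procedure (an inference), time at risk is unequal and the comparison generally leans toward no harm.

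- **Earliest-date reading:** the bias is confined to device-related adverse events and other outcomes after 6 months, for fractures first seen at 36 months.
- **Detection-date reading:** every fracture found on a scheduled film is affected.

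On the assumed rates, the no-effect ratio for late-detected fractures is 0.30 to 0.86, or about 0.83 to 0.96 pooled with a quarter late. A true doubling reads about 0.45 to 1.28, against about 1.5 with a matched start. These figures are illustrative, because the documents give no event rates, fracture frequency or horizon for this analysis. It is an additional analysis outside the test hierarchy, and the primary tests are unaffected.

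**What to change.** Amend section 4.9.1 as follows.

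1. Define the fracture date as the earliest possible date, that is, the last fracture-free image. Use the detection date as a sensitivity analysis.
2. Keep the 6-month analysis counted from the procedure in both subgroups. State that 6-month closure is compared by fracture status without the onset rule.
3. For reports after 6 months, start both subgroups at the same point. Count events after the 6-month film by fracture status at that film. For fractures first seen at 36 months, count both subgroups from the 6-month film. An alternative is fracture as a time-dependent status, with earlier events and time assigned to no fracture.
4. List earlier events separately, and report estimates with confidence intervals.

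The cost is SAP wording and some programming, with no new data. Precision will be low. With 30% fractured (assumed), e = 3%, l = 2% and no effect, subjects event-free at the film number N × 0.962 × 0.30, and their later risk is 4.94%. Expected fracture-group events are about 1.8 for the 125 pivotal subjects, 6.6 for the SAP's 460, and 9.4 for the 660 non-training subjects (125 + 535) in Protocol Revision 6. Counting from the 6-month film also has almost no follow-up at the time of the pre-market submission, which is why item 2 keeps the procedure as the origin there.
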